#### **9.2.1.3. ts/bDMARD-naïve RA Cohort**

- At least two separate visits documented in Swedish Patient Register listing RA as a diagnosis code for the visit, with at least one visit at a unit of Rheumatology or Internal Medicine.
- Patients are censored from this cohort when they start tofacitinib or a bDMARD, but are eligible for subsequent inclusion into the respective drug-based cohorts defined above.
- To ensure a contemporaneous cohort, diagnosis of RA must have occurred after 01 January 2012.

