### 9.3.2. Follow-Up

Subjects will be followed from treatment start (or for comparator cohorts not defined by therapy: from an index date) until each outcome of interest, with death and emigration from Sweden treated as censoring events.

Some outcomes of interest in this study are thought to potentially occur at a higher rate while on drug, but that increased risk subsides after the drug is discontinued (ie, serious infections, herpes zoster, CV events, gastrointestinal (GI) perforation, progressive multifocal leukoencephalopathy (PML)). Those events will be evaluated over a risk window that includes time from drug initiation until 90 days after end of treatment. When a patient initiates a new therapy within the 90-day extension, the time and events during the overlapping period will be assigned to both treatments. The 90-day extension period is implemented in part to accommodate ongoing exposure to treatments with longer half-lives, and in part to ensure that any subclinical or undiagnosed illness at time of end of treatment is captured. As an additional sensitivity analysis for MACE, MI, serious infection, VTE, herpes zoster, PML, and gastrointestinal perforation events with a 90-day extension period applied after treatment discontinuation, if a new medication is started during the 90-day window after discontinuation of a previous medication, initiation of the new medication will stop the 90-day risk window, and any event prior to the new medication start will be assigned to the discontinued medication. Similarly, as part of the primary analysis, for malignancy and all-cause mortality events, a 90-day risk window will be applied to the censoring at switch approach (i.e., if a malignancy or death occurs in first 90 days after a patient has switched to a different therapy, follow-up time and the event will be attributed to prior therapy and not current therapy).

For non-melanoma skin cancer (NMSC), lung cancer, lymphoma and malignancies excluding NMSC, and all-cause mortality, the manifestation of which is expected to be delayed relative to the time of exposure, the outcomes will be evaluated using two different approaches, a once exposed always at risk approach as the primary analysis and a censor at switch approach as a secondary analysis. PML rates will also be described using this approach.

---

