 The potential mechanism for increased PML risk is poorly understood. PML will be evaluated using both on drug and once-exposed always at risk approaches.

The primary analysis will assume a once exposed always at risk paradigm, as is frequently used in study of malignancy risk due to bDMARDs. Under this approach, follow up for each cohort continues from the cohort index date until the first of a malignancy event, loss to follow up, death or end of study. Follow up for each exposure cohort continues after switching to a new drug or discontinuation of treatment. This approach maximizes follow up time and the ability to capture long latency events, ie, events that occur or are detected years after exposure. Under this approach, events will be double-counted if a patient indexed to bDMARD switches to tofacitinib and a malignancy occurs subsequent to tofacitinib exposure. That is, the event will be assigned to both the bDMARD and the tofacitinib exposure cohorts as will the corresponding person years since index to the respective cohorts. Because tofacitinib is expected to be used as a later line therapy, switching is expected to be non-random with most tofacitinib patients having been included in the bDMARD cohort prior to initiation of tofacitinib. In such cases, the bDMARD rate will have more associated person-years and thus a relatively lower rate than the corresponding rate in the tofacitinib cohort.

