Using this primary analytic approach, if neither tofacitinib nor bDMARDs cause an increased risk of malignancy both exposure cohort rates will reflect the background rates of malignancy from the time of index to the end of the study period and the comparative effect measure will indicate no difference in rates. If tofacitinib does cause an increased rate of malignancy, which is the effect we are most interested in detecting, a relatively higher rate will be observed in the tofacitinib exposed cohort. The once exposed always at risk approach is therefore able to detect an increased rate given the non-random switching expected to occur given use of bDMARDs prior to tofacitinib and is consistent with previous studies evaluating the risk of individual biologics. Additional analyses will be conducted to evaluate potential confounders and the impact of different latency assumptions as will be described in the statistical analysis plan (SAP). Sensitivity analyses will be conducted that restrict the bDMARD comparator cohort to patients who were never exposed to tofacitinib or other non-biologic advanced therapies and compare the characteristics of those bDMARD patients ever and never exposed to tofacitinib.

Secondary analyses that censor follow up time after a switch to a different treatment class will also be performed. Among patients indexed to a bDMARD cohort, follow up will begin at index and continue until the first of an event, switch to tofacitinib or other non-biologic advanced systemic therapy, loss to follow up, death, or study end date. Similarly, for tofacitinib, follow up will begin at index and continue until the first of an event, switch to a non-JAK inhibitor-based advanced systemic therapy, loss to follow up, death or study end date. While this approach eliminates the problem of double counting, it may not allow sufficient follow up time to allow for latent effects or detection and decreases the number of events included reducing the statistical power to detect a higher risk of malignancy in tofacitinib treated patients. However, under an assumption of no latency or a very short latent period as in an aggressive tumor promoter, this approach would detect an increased risk of disease on tofacitinib relative to the risk due to bDMARDs.

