Of note, several studies compared a once-exposed approach to a time on drug and other approaches and found similar rates of malignancy using an on-drug and ever-exposed approach.

The schematic below provides examples of patterns of event and treatment patterns to illustrate resulting contribution to rate calculation in the once exposed always at risk and censoring at switch analytic models:

- \*: bDMARD index date;
- ~: year on bDMARD;
- ^: tofacitinib index date;
- : year on tofacitinib;
- O: discontinuation of advanced systemic therapies;
- =: year not on systemic therapy;
- X: event.

Treatment/Event pattern	Once-exposed always at risk		Censoring at Switch	
	bDMARD rate contribution (events/person years)	Tofacitinib rate contribution (events/person years)	bDMARD rate contribution (events/person years)	Tofacitinib rate contribution (events/person years)
* ~ ~ ~ ^ - - X	1/5	1/2	0/3	1/2
* ~ ~ ~ X	1/3	0/0	1/3	0/0
^ - - - O = = = X	0/0	1/6	0/0	1/6 a
* ~ ~ ~ ^ - - - ~ ~ ~ X	1/9	1/6	0/3	0/3
^ - - - - ~ ~ ~ X	0/0 b	1/7	0/0 b	0/4

- a. Patients continue to be followed after index exposure discontinuation if they do not initiate another systemic therapy in a different class.
  - b. Patients are ineligible for bDMARD cohort index after tofacitinib index.
- Note: if an event does not occur, person time will be allocated to rate denominator as described in table without corresponding event.

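### In the secondary censor-at-switch analysis, the 90-day carry-back opens malignancy follow-up at about day 90 for most tofacitinib starters but at day 0 for bDMARD starters, and it contradicts the same section's follow-up definition and worked examples

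*Protocol*

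**What the plan says.** All of this is in protocol section 9.3.2 unless noted.

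- For malignancy and all-cause mortality, "a 90-day risk window will be applied to the censoring at switch approach". The rule operates "if a malignancy or death occurs in first 90 days after a patient has switched to a different therapy"; then "follow-up time and the event will be attributed to prior therapy and not current therapy".
- The sentence that introduces the rule places it in the primary analysis. The next paragraph makes once-exposed-always-at-risk primary and censor-at-switch secondary.
- The switch is defined by class: "Secondary analyses that censor follow up time after a switch to a different treatment class will also be performed". Follow-up in both drug cohorts is described as starting at the index date.
- On the route into tofacitinib: "switching is expected to be non-random with most tofacitinib patients having been included in the bDMARD cohort prior to initiation of tofacitinib".
- Footnote b to the worked examples: "Patients are ineligible for bDMARD cohort index after tofacitinib index".
- Section 9.2.1.3, on the naive cohort: "Patients are censored from this cohort when they start tofacitinib or a bDMARD". No carry-over is given for these patients.
- The worked examples give events per person-years for five patterns. The first (three years on bDMARD, two on tofacitinib, then an event) is 0/3 for bDMARD and 1/2 for tofacitinib under censoring at switch.

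**The concern.** The rule is worded the same for both arms but acts on them differently. A tofacitinib starter with a prior bDMARD has changed class, so days 0-90 go back to the bDMARD arm. A first-bDMARD starter has no prior advanced therapy to carry back to. A bDMARD-to-bDMARD change is not a class switch, and in a pooled bDMARD arm it would stay in the same arm anyway. Footnote b means that no patient going from tofacitinib to a bDMARD can lose early days in the bDMARD arm. Only the few bDMARD starters coming from another non-biologic advanced therapy could.

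The two arms then have different windows after index. This matters if detection or hazard just after a treatment start differs from later, as it would if disease already present is found at that point. The section justifies censor-at-switch as able to detect a tofacitinib effect with little or no latency, yet the carry-back sends the earliest events after most tofacitinib starts to the comparator. The outcomes include lung cancer and lymphoma, which section 7.2 lists as identified risks.

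**Working it through.** **Step 1: reproduce the worked examples.** Starting at index and stopping at a class switch gives exactly the stated contributions (bDMARD, tofacitinib): 0/3 and 1/2; 1/3 and 0/0; 0/0 and 1/6; 0/3 and 0/3; 0/0 and 0/4. With a 90-day carry-back (90/365.25, about 0.25 y):

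- Pattern 1 becomes 0/3.25 and 1/1.75.
- Pattern 4 becomes 0/3.25 and 0/3.00. Tofacitinib loses 0.25 y at the start and gains 0.25 y after the switch off.
- Pattern 5 becomes 0/0 and 0/4.25.
- Patterns 2 and 3 do not change.

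The published figures therefore hold only without the rule. In no pattern does a bDMARD starter lose days 0-90.

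**Step 2: inputs for size.** Section 9.5 gives 30% switching off tofacitinib per year, 5% loss per year and constant accrual. It states a 7-year study in the text and 5 years in the titles of Tables 2 and 3, so both are run. Three inputs are assumptions:

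- the share s of tofacitinib starters coming from bDMARDs is 60-100% (the protocol says only that it is most);
- the hazard in the first 90 days after any start is k times the later hazard;
- bDMARD class exit, for which no rate is given, is either the same as for tofacitinib or zero.

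Exit hazard: -ln(0.70) - ln(0.95) = 0.357 + 0.051 = 0.408 per year. Averaged over uniform entry, in years per patient for 5-year / 7-year studies:

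- M, mean follow-up to switch: 1.406 / 1.642
- e, mean time in days 0-90: 0.229 / 0.230 (16.3% / 14.0% of M)
- t, mean time in the 90 days after a switch off: 0.119 / 0.141
- without attrition, mean follow-up F = 2.5 / 3.5 and e0 = 0.240 / 0.242 (9.6% / 6.9% of F)

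**Step 3: null ratio when time moves with events.**

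- Tofacitinib: [(M - e) + (1 - s)ke + kt] / [M - se + t]
- bDMARD, equal exit: [(M - e) + ke + kt] / [M + t]
- bDMARD, no attrition: [(F - e0) + k·e0] / F (the small transfer of tofacitinib days into this arm is ignored)

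Example (5 years, k = 2, s = 1): tofacitinib 1.415/1.296 = 1.092; bDMARD with equal exit 1.872/1.525 = 1.228; ratio 0.889. Against bDMARD without attrition (1.096) the ratio is 0.996.

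| k | Equal exit, s = 60% to 100% (5 y; 7 y) | No bDMARD attrition, s = 60% to 100% (5 y; 7 y) |
|---|---|---|
| 0.5 | 1.04 to 1.08; 1.04 to 1.07 | 0.97 to 1.00; 0.96 to 0.99 |
| 1 | 1.00; 1.00 | 1.00; 1.00 |
| 2 | 0.94 to 0.89; 0.95 to 0.90 | 1.05 to 1.00; 1.07 to 1.02 |
| 3 | 0.90 to 0.81; 0.91 to 0.83 | 1.09 to 0.99; 1.13 to 1.04 |

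Without bDMARD attrition the ratio differs from 1 even with no carry-back, because early days are a larger share of the shorter tofacitinib follow-up: at k = 2, 1.163/1.096 = 1.06 and 1.140/1.069 = 1.07.

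**Step 4: the literal trigger.** The rule is conditional on an event. If time moved only for patients with an event, the ratio would leave 1 even at k = 1. With equal exit it is roughly 1 - se/(M + t), which is 0.91 to 0.85 (5 years) or 0.92 to 0.87 (7 years) for s = 60% to 100%.

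**The case against.** Several objections have force.

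- A reader might infer that the rule always lowers the tofacitinib/bDMARD ratio. The documents do not support that. They give no early hazard; at k = 1 the ratio is 1.00, at k below 1 the equal-exit bias reverses, and without bDMARD attrition it is close to 1 or above.
- A reader might size the effect from the lost days alone, with every tofacitinib patient a switcher: 1/(1 + 0.163) = 0.86 at k = 2, or 1/(1 + 2 × 0.163) = 0.75 at k = 3, in a 5-year study. That omits the 90 days tofacitinib regains after a switch off, and the protocol says most, not all.
- A reader might take this as the only malignancy analysis free of double counting. It is not: section 9.3.2 also plans a sensitivity analysis with a bDMARD comparator never exposed to tofacitinib.
- The rule's own trigger is a switch to a different therapy, not a different class. On that wording second- and third-biologic starters also lose days 0-90 to their prior drug. In the line-specific shells of Appendix 2 (Table IV is stratified by number of previous biologics), windows could then match within a stratum. This stands for those tables; it does not help the pooled contrast.
- Latency variants are left to the SAP. That covers alternative lags, but this allocation rule is fixed in the protocol and conflicts with its own text there.

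If the index-start wording and the worked examples govern, the unequal start disappears. That is a reason to reconcile the passages, not to leave them.

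**Conclusion.** The point holds for the secondary censor-at-switch analysis in a pooled tofacitinib versus bDMARD comparison. Taken together, the carry-back, the class definition of a switch, the expected route into tofacitinib and the bar on later bDMARD entry give unequal windows after index. The text is also inconsistent on when follow-up starts, on the worked contributions (0/3 and 1/2 against 0/3.25 and 1/1.75), and on whether the rule is primary or secondary.

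The possible bias is moderate and conditional: a null ratio of about 0.89-0.95 (k = 2) or 0.81-0.91 (k = 3) with equal exit rates, about 0.99-1.13 without bDMARD attrition, and exactly 1.00 at a constant hazard with time and events moved together. These figures rest on assumed k, s and bDMARD exit rates. A reader might carry the concern over to the primary malignancy result; once-exposed-always-at-risk follow-up runs from index through any switch, so it is not affected. The change should be made, but the study's main malignancy analysis does not depend on it.

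**What to change.** In section 9.3.2:

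1. Reconcile the carry-back rule, the start-at-index wording and the worked examples, and state that the rule belongs to the secondary analysis.
2. In that analysis, start malignancy follow-up at day 90 after index in both drug cohorts, whatever the prior therapy, with the same 90-day extension after a class switch in both.
3. State that person-time moves for all switchers, not only for those with an event.
4. Report days 0-90 separately by cohort.
5. Show the result without carry-back (start at index, stop at switch) as a sensitivity analysis.

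With equal exit rates this brings the null ratio to 1.00 for any k. It equalises the start only. If bDMARD patients rarely leave their class, the extension after a switch still adds early-window time mainly to tofacitinib: (M - e + kt)/(M - e + t) = 1.415/1.296 = 1.09 at k = 2 in the no-attrition extreme. Items 4 and 5 are needed so that readers can see this.

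The cost is a short text change and a shifted start date in the code. Roughly 7-16% of bDMARD person-time, with the corresponding events, leaves this secondary analysis.

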### **9.7.1. Semi-Annual Reports**

Reports summarizing the rate of safety events of interest will be provided by ARTIS to Pfizer on a semi-annual basis, with tables corresponding to the template Appendix 1. These will provide data from SRQ/ARTIS on the patients treated with tofacitinib and rates “on drug” and “ever since treatment start”, but they will not contain comparator cohorts or adjusted comparisons.

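### All-cause mortality is classed wholly as a delayed outcome, so it has no tofacitinib-versus-comparator analysis limited to on-drug time plus 90 days

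*Protocol*

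**What the plan says.** Section 9.3.2 sorts outcomes by the assumed timing of risk.

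- **On-drug outcomes.** For serious infections, herpes zoster, cardiovascular events, gastrointestinal perforation and PML, the rate may be raised on treatment, "but that increased risk subsides after the drug is discontinued". The rule is: "Those events will be evaluated over a risk window that includes time from drug initiation until 90 days after end of treatment".
- **Delayed outcomes.** The next paragraph takes the cancers together with death: "and all-cause mortality, the manifestation of which is expected to be delayed relative to the time of exposure". These get "a once exposed always at risk approach as the primary analysis and a censor at switch approach as a secondary analysis".
- **Primary analysis.** "Follow up for each exposure cohort continues after switching to a new drug or discontinuation of treatment".
- **Secondary analysis.** Follow-up stops at a switch of class. For malignancy and death, the first 90 days after a switch are credited to the previous therapy. Note a to the schematic keeps a patient under observation after stopping if no other class is started.
- **Both windows.** Footnote 2 says: "PML will be evaluated using both on drug and once-exposed always at risk approaches". No other outcome is given both.

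Section 9.7.1 foresees on-drug rates for tofacitinib in the semi-annual reports, "but they will not contain comparator cohorts or adjusted comparisons". Appendix 4 defines MACE to include any death with an I00-I99 code as main cause.

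**The concern.** Deaths from infection, cardiovascular disease or perforation are part of all-cause mortality. Section 9.3.2 thus makes two different timing assumptions about the same deaths: the fatal event belongs to a risk that fades after stopping, yet the death is expected to be delayed. The argument for always-at-risk in 9.3.2 is about the latency and detection of malignancy. None is given for death as a whole.

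If tofacitinib raised mortality mainly while it is taken, an analysis that also counts time long after stopping would average that excess with time at background risk. The estimate would move towards 1, and no compared analysis of total mortality restricted to the exposed period would stand beside it.

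**Working it through.** **1. The plan's own schematic (9.3.2).** Row three has 3 years on tofacitinib, 3 years untreated, then an event. Person-time is 3 + 3 = 6 years, so the contribution is 1/6. The protocol prints 1/6 under both approaches, which is reproduced. Under the 90-day window the same patient gives 0/(3 + 0.25) = 0/3.25. Row four has a tofacitinib patient who moves to a bDMARD and has the event 3 years later. It scores 1/6 always-at-risk and 0/3 at censoring. The secondary analysis therefore handles switchers but not untreated stoppers.

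**2. Inputs for the dilution.**
- Switching off tofacitinib at 30% a year (9.5), used here as the rate of all stopping. Read as a yearly proportion, the hazard is s = -ln(0.7) = 0.357; read as a rate, s = 0.30.
- Loss to follow-up of 5% a year (9.5), or none.
- Study length T of 7 years (9.5 text) or 5 years (titles of Tables 2 and 3), with uniform accrual.
- w = 90/365.25 = 0.246 years.
- Assumption: constant hazards, with the off-drug hazard equal to the comparator's.

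**3. On-drug plus 90-day share of always-at-risk time.** With no loss, mean total follow-up is T/2. The mean time in the window is

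(1/T) × [w²/2 + w(T - w) + ((T - w) - (1 - exp(-s(T - w)))/s)/s].

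For T = 7 and s = 0.357 this is (0.030 + 1.664 + 11.78)/7 = 1.925 years. The share is 1.925/3.5 = 0.55. Loss was added by numerical integration.

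| T | s = 0.357, no loss | s = 0.357, 5% loss | s = 0.30, no loss | s = 0.30, 5% loss |
|---|---|---|---|---|
| 5 | 0.65 | 0.66 | 0.69 | 0.70 |
| 7 | 0.55 | 0.57 | 0.59 | 0.61 |

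**4. Averaged hazard ratio, primary analysis.** Averaged HR = 1 + share × (HR - 1), a person-time average that approximates the Cox estimate.
- HR 2.0: 1.65 to 1.70 (5 years); 1.55 to 1.61 (7 years).
- Sensitivity over 7 years with 5% loss: 1.83 at 10% annual stopping, 1.48 at 40%.

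**5. Averaged hazard ratio, censor at switch.** Let q be the fraction of stoppers who start nothing else. The documents give no value, so 10% to 50% is assumed, with switchers changing drug when they stop and censored 90 days later. The share becomes on/(on + q × (total - on)).
- T = 7, s = 0.357, no loss, q = 0.10: 1.925/(1.925 + 0.1575) = 0.92, so HR 2.0 averages 1.92.
- Same, q = 0.50: 1.925/(1.925 + 0.7875) = 0.71, so 1.71.
- Same s with 5% loss: 1.93 and 1.73.
- s = 0.30: 1.94 at q = 0.10, and 1.75 to 1.76 at q = 0.50.
- q = 0: no dilution.

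**The case against.** The strongest reply is that the planned secondary analysis does most of the work. The 30% in section 9.5 is switching from tofacitinib to a bDMARD, and those patients are exactly the ones censored at switch. If every stopper switched, the secondary would carry no off-drug time beyond the 90 days. This stands. The 1.55 to 1.70 figures describe the primary only, and the secondary is weakened only by untreated stoppers.

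Fatal cardiovascular events, including any thromboembolic death coded within I00-I99, are compared over the on-drug window through MACE. This also stands and narrows the gap.

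Always-at-risk is a defensible primary. All-cause mortality includes cancer deaths, and stopping treatment in terminal illness makes on-drug mortality hard to interpret. This stands as a reason to keep the primary, not as a reason to have no on-drug comparison beside it.

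The remaining reply is that exposure windows belong in the SAP. Annex 2 says the SAP will describe how exposure is accounted for, and 9.3.2 leaves other latency assumptions to it in the discussion of malignancy. The SAP may add an analysis, but the protocol itself assigns mortality to the delayed class and names its two analyses. That classification is what needs correcting.

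**Conclusion.** The point holds in a limited form. Classing mortality as delayed in its entirety conflicts with the timing that section 9.3.2 gives to several causes of death, and it leaves total and non-cardiovascular mortality without a compared on-drug plus 90-day estimate. A true on-drug HR of 2.0 would average about 1.65 to 1.70 (5 years) or 1.55 to 1.61 (7 years) in the primary, and about 1.93 down to 1.73 over 7 years in the secondary. These sizes rest on 30% annual stopping, an off-drug hazard equal to the comparator's and, for the secondary, the assumed 10% to 50% of untreated stoppers.

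A reader might infer more than this, and the documents do not support it:
- That the plan as a whole would miss a mortality excess. A power comparison of always-at-risk with on-drug analysis (for instance 0.34 against 0.53 for an HR of 1.5) ignores the planned secondary and rests on one assumed comparator mortality of 10 per 1000 person-years, which is not in the protocol.
- That fatal harms are less detectable than non-fatal ones throughout. MACE already contains the fatal cardiovascular events.
- That no on-drug mortality rate can exist. Section 9.7.1 foresees on-drug rates for tofacitinib; what is missing is the comparison.

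**What to change.** In section 9.3.2:
- Add all-cause mortality as a supplementary endpoint over initiation to 90 days after end of treatment, with the same rule in the tofacitinib and bDMARD cohorts. Report it beside the unchanged always-at-risk primary, as is already done for PML.
- Limit the statement that manifestation is expected to be delayed to the malignancies.
- While editing, reconcile the sentence that calls the 90-day rule for malignancy and death part of the primary analysis with the next paragraph, which makes censor at switch secondary.

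The cost is a few words and one more run of a window already specified for other endpoints. The new estimate is sensitive to patients stopping treatment in terminal illness, whose deaths may fall after day 90. It should therefore be labelled supplementary and read with the primary, not in place of it.
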